## **STUDY RATIONALE AND JUSTIFICATION: LOW LEVEL LASER THERAPY AS A TREATMENT FOR TOENAIL ONYCHOMYCOSIS**

Presently, there is no perfect cure for toenail fungus. Even the most effective oral medications are successful only about half of the time. Topical medications are successful less than 10% of the time. As 10% of the adult population is affected by toenail onychomycosis, the need for a more effective and lasting cure is evident.

Recently, application of low level laser therapy to the affected toenail over a four-week period using the Erchonia® LunulaLaser™ device has been clinically demonstrated to effect increase in clear nail in onychomycosis-infected toenails, and the device subsequently received FDA clearance to be marketed for this indication (K153164) based on this clinical outcome.

Unlike medication-driven treatments for toenail fungus which can have many side effects including serious ones such as liver toxicity, low level laser therapy presents minimal risk of side effects. Laser therapy is applied to toenail onychomycosis by shining a laser light through the toenail. The laser light vaporizes the fungus while leaving the skin and surrounding tissue unharmed, in a simple, quick, non-invasive and pain-free manner.

The goal of this current study is to expand the present indication for use for the Erchonia® LunulaLaser™ of: “The LunulaLaser™ device is indicated for use for the temporary increase of clear nail in patients with onychomycosis (e.g. dermatophytes *Trichophyton rubrum* and *T. mentagrophytes*, and/or yeasts *Candida albicans*, etc.)” (K153164) from the aesthetic claim of changing the nail appearance to the medical claim of eradicating the underlying fungal infection. As such, this clinical study protocol design is intended to provide data to support an indication for use of ‘treatment of onychomycosis’ through application of the Erchonia® LunulaLaser™.

Prior clinical trials evaluating application of the Erchonia® LunulaLaser™ to toenail onychomycosis have reported negative culture results at completion of treatment administration, providing support and justification for conducting a controlled clinical trial to specifically assess and support a claim of treatment of onychomycosis for the Erchonia® LunulaLaser™ device.

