## **TREATMENT ADMINISTRATION PHASE**

### **GENERAL ASSESSMENT CONDITIONS**

Subjects must agree to not partake in any non-study treatment(s) for toenail onychomycosis (including oral medications and nail lacquer, non-alternative therapies such as acupuncture and home remedies), or to use any toenail cosmetics throughout the course of study participation.

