### **PRIMARY EFFICACY OUTCOME EVALUATION**

The primary efficacy outcome measure in this study is the Complete Cure Rate at study endpoint.

Individual Subject Success Criteria: 'Complete Cure' criteria is defined as a subject/toenail satisfying both the 'Clinical Cure' and the 'Mycological Cure' criteria in order to be considered a study responder, defined as follows:

(i) Clinical Cure: Measurement of clear nail increase as the following:

- at least 12 mm increase in clear nail of the great toenail, with evidence of distal growth of the affected area, 12 months after the first treatment;  
or
- complete clearance 12 months after the first treatment if less than 12 mm distal nail was involved prior to treatment.

The response should be progressive in at least 2 sequential timepoints that are at least 3 months apart, with projected increase of at least 1 mm per month.

(ii) Mycologic Cure: Negative Fungal Culture results

Overall Study Success Criteria is defined as both of:

(i) a minimum 70% Clinical Cure Clear Nail Responder Rate;

AND

(ii) Among toenails which are deemed responders based on the Clinical Cure Clear Nail criteria, at least 80% will also demonstrate Mycological Cure.

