## **PRIMARY EFFICACY OUTCOME STATISTICAL EVALUATION METHODS**

- **Intent to Treat (ITT) Principle:** Primary efficacy analysis will be according to the intent to treat (ITT) principle; wherein subjects will be included in the analysis if they had a valid Baseline Assessment visit.
- **Missing data** will be handled through *Last Observation Carried Forward (LOCF)*: by carrying forward the last recorded observation to fill in the subsequent missing value.

Subjects who drop out or are lost to follow-up will be considered as treatment failures (non-responders) in the statistical evaluation.

- **Per-Protocol Analysis** will also be performed for the set of all subjects who completed the study according to the full protocol.
- **Primary analysis of efficacy** according to *intent to treat* (ITT) analysis will be through determination of satisfaction of the Overall Study Success Criteria.

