## **EVALUATION OF SUBJECT DAILY DIARY MEASURES**

The information recorded by the subjects in the Subject Daily Diary on each day of the study evaluation period will be evaluated as follows:

- The impact on study outcome of reported notable non-compliance with other (non-study) toenail fungus treatment abstinence.
- The impact on study outcome of reported notable non-compliance with abstinence from use of toenail cosmetics on the study great toenail(s)
- Any changes in medication and therapy use across study progression relative to that reported at baseline and the impact on study outcome.
- Any potential perceived adverse events will be reported and evaluated
- Any comments provided by subjects will be reported and evaluated.

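### The primary ITT count credits the laser with any cure produced by a non-study antifungal, which in a single-arm trial can bias the result only towards success

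*Combined protocol and SAP*

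**What the plan says.** Under Primary Efficacy Outcome Evaluation, a subject or toenail succeeds by "satisfying both the 'Clinical Cure' and the 'Mycological Cure' criteria in order to be considered a study responder". Clinical Cure is a nail measurement and Mycological Cure is a negative culture. Neither carries a condition about other treatment. Study success needs at least 70% Clinical Cure and, among those clinical responders, at least 80% with Mycological Cure. Study End Point Evaluation places both at 12 months.

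Under Primary Efficacy Outcome Statistical Evaluation Methods, the ITT rule is that "subjects will be included in the analysis if they had a valid Baseline Assessment visit". Missing data are handled "by carrying forward the last recorded observation to fill in the subsequent missing value", and "Subjects who drop out or are lost to follow-up will be considered as treatment failures (non-responders) in the statistical evaluation". A per-protocol analysis "will also be performed for the set of all subjects who completed the study according to the full protocol", with no list of disqualifying deviations.

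Other treatment is addressed in four other places. Willingness to abstain is an inclusion criterion. General Assessment Conditions states that "Subjects must agree to not partake in any non-study treatment(s) for toenail onychomycosis". The Subject Daily Diary records abstinence and any change in medication. Evaluation of Subject Daily Diary Measures will assess the effect on outcome of "reported notable non-compliance with other (non-study) toenail fungus treatment abstinence" and, in a separate bullet, of any change in medication or therapy since baseline.

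Study Treatment Group states that all subjects receive active laser treatment, with no control group.

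**The concern.** The protocol treats other antifungal therapy as a confounder. It excludes recent oral and topical use at entry, requires abstinence afterwards and checks it daily. The primary responder definition then gives a breach no consequence. Someone who leaves the study is a failure, while someone who stays, takes an antifungal and clears is a success.

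A concurrent control arm would show what background antifungal use contributes to the cure rate. Here nothing does. The study is meant to support a move from a claim about nail appearance to one about eradicating the infection, so attributing cure to the laser is the central question. Follow-up lasts a year, and subjects who see no improvement have a reason to look elsewhere. The threshold has no confidence margin, so a single subject can decide the clinical limb.

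**Working it through.** **Inputs from the documents.** Base sample 60, dropout one-twelfth, enrolment 66 (Rationale for sample size). Clinical threshold 70% (Primary Efficacy Outcome Evaluation). Drug success, from Study Rationale and Justification: "Even the most effective oral medications are successful only about half of the time", and under 10% for topical medications.

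**Assumptions, not in the documents.** True laser-only clinical cure rate p = 0.65 over all 66 subjects. Proportion using a non-study antifungal u = 5%, 10% or 15%. Proportion of would-be failures rescued r = 0.10 (upper end of the topical figure) or 0.50 (oral figure).

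**Step 1, the plan's own figure.** 60 / (1 − 1/12) = 65.45, rounded up to 66. This reproduces.

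**Step 2, the threshold in subjects.** 0.70 × 66 = 46.2, so 47 responders are needed. 47/66 = 71.2% passes and 46/66 = 69.7% fails. Each subject is worth 1/66 = 1.5 percentage points.

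**Step 3, observed-outcome scoring, use spread evenly.** The counted rate is p + u × (1 − p) × r, and the chance of passing is the exact binomial P(X ≥ 47 | n = 66). With no use, p = 0.65 gives 17.7%.

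| Use u | Rate, r = 0.10 | Chance | Rate, r = 0.50 | Chance |
|---|---|---|---|---|
| 5% | 0.65 + 0.05 × 0.35 × 0.10 = 0.652 | 18.5% | 0.65 + 0.05 × 0.35 × 0.50 = 0.659 | 21.8% |
| 10% | 0.654 | 19.3% | 0.668 | 26.4% |
| 15% | 0.655 | 20.1% | 0.676 | 31.6% |

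**Step 4, use concentrated in failing subjects.** If the 5% who use a drug are all would-be failures and half are rescued, the rate is 0.65 + 0.05 × 0.50 = 0.675 and the chance is 30.8%.

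**Step 5, every user scored as a non-responder.** If use is independent of response, the rate is p × (1 − u). At 10% use this is 0.65 × 0.90 = 0.585, and the chance of passing is 2.3%. If all users are would-be failures, the rate stays at 0.65.

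These figures cover the clinical limb only. The culture limb was not modelled.

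**The case against.** A reader might infer that the plan does inflate the cure rate. The documents do not support that. They give no rate of use, and the gap arises from silence, not from an explicit permission. Inflation needs use, completion, and a cure the laser would not have produced.

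A reader might also infer that an antifungal taken for a reason other than onychomycosis would go unseen, because the abstinence rule does not cover it. It would not: the diary records every medication change, and the diary evaluation assesses the effect of such changes on outcome. What stands is that neither step alters the primary count. It also stands that notable non-compliance is undefined and that such a subject could remain in the per-protocol set.

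Some users might be terminated and so become failures. The sample-size rationale expects some terminations, but no section makes antifungal use a ground for one. The only disqualification stated during treatment is for not re-inserting the foot.

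The size is open to fair challenge. Applying the oral figure to every user would overstate the effect of topical use. The rationale's undefined success is also not the trial endpoint, which needs a 12 mm gain or complete clearance at month 12 and a progressive response over at least 3 months. Rescue begun late may not qualify. In the other direction, an even spread of use understates the effect if failing subjects are the ones who seek treatment.

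The failure rule for dropouts also sits beside last observation carried forward, with no statement of which governs. That is a separate ambiguity and does not affect completers.

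Finally, observed-outcome ITT with a defined sensitivity analysis is a recognised alternative to non-responder scoring, though weaker without a control arm.

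**Conclusion.** The point holds as a gap in the primary scoring rule. A completer cleared by a non-study antifungal counts as a laser cure, and the existing safeguards reveal this without correcting it. Because such cures can only add to the numerator and there is no comparator, any resulting error favours success. At the margin, one re-scored subject turns 47/66 into 46/66 and reverses the clinical limb.

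The amount of inflation is unknown. Under the stated assumptions, even use by 5% to 15% of subjects raises the chance of meeting the clinical limb by about 1 to 2 percentage points at 10% rescue, and by about 4 to 14 points at 50% rescue. Concentration in failing subjects makes it larger. These are illustrations that depend on the assumed 65% rate, the rates of use and the rescue fractions. They are not estimates for this trial.

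**What to change.** Add to Primary Efficacy Outcome Statistical Evaluation Methods: a subject with recorded use, between the first treatment and the 12-month evaluation, of a non-study treatment for onychomycosis of the target toenail, or of a systemic antifungal taken for another reason, is a non-responder in the primary analysis. Say that this means not attaining Clinical Cure, so that the subject also leaves the denominator of the 80% culture criterion. List the same uses as per-protocol deviations, and report scoring by observed outcome as a sensitivity analysis. Settle this before outcome data are reviewed.

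This changes scoring only. It uses diary and medication data already collected and leaves treatment, visits and enrolment as they are.

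The cost is conservatism. The rule also fails users whom the laser would have cured, including subjects who broke no rule because they took a systemic antifungal for another condition. The loss is small if use is rare or mostly among failing subjects. At 10% use independent of response it is not small: the expected rate falls from 65% to 58.5%, and the chance of meeting the clinical limb from 17.7% to 2.3%. The sensitivity analysis lets a reader see both bounds.

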## **SECONDARY EFFICACY OUTCOME EVALUATION**

The pre-specified secondary efficacy endpoints are

- (i) Clinical Efficacy Rate at week 52, defined as < 10% affected target nail area
- (ii) Mycological Cure Rate at week 52 (negative culture), and
- (iii) Unaffected New Nail Growth at week 52 (change from baseline in healthy nail measurement).

Secondary endpoints will be measured in sequential order.

## **ADDITIONAL SUPPORTIVE OUTCOME EVALUATIONS**

- Responder Rates across progressive evaluation visits
- Percentage of clinical onychomycosis involvement determinations across progressive evaluation visits
- Change in mm clear nail across progressive evaluation visits.

## **SUBGROUP AND COVARIATE ANALYSES**

Study outcome will also be performed for the following subgroups and covariates, as applicable:

- Study test site
- Category of % of baseline toenail onychomycosis involvement:
  - 20%-34% toenail onychomycosis involvement
  - 35%-50% toenail onychomycosis involvement
- Baseline Fungal Culture Results Category according to type of organism identified.
- Baseline % of toenail onychomycosis disease involvement
- Right versus left great toenail
- Duration of toenail onychomycosis at baseline
- Age
- Gender
- Ethnicity

## **EVALUATION OF SUBJECT DAILY DIARY MEASURES**

The information recorded by the subjects in the Subject Daily Diary on each day of the study evaluation period will be evaluated as follows:

- The impact on study outcome of reported notable non-compliance with other (non-study) toenail fungus treatment abstinence.
- The impact on study outcome of reported notable non-compliance with abstinence from use of toenail cosmetics on the study great toenail(s)
- Any changes in medication and therapy use across study progression relative to that reported at baseline and the impact on study outcome.
- Any potential perceived adverse events will be reported and evaluated
- Any comments provided by subjects will be reported and evaluated.

## **SAFETY ANALYSES**

Safety analyses will be based on all subjects who signed the informed consent form and were enrolled in the study. Safety will be assessed by evaluating the incidence, frequency and severity of observed and/or reported adverse events. Specific safety evaluation will be made with respect to re-infection rate, as applicable. Safety evaluation will be conducted for all toenails on the study treated foot, as applicable.

## **INFORMED CONSENT**

- Informed consent will be an agreement between the individual investigator and each subject, having the capacity to understand and make an informed decision. Consent will be obtained prior to each potential subject's participation in this clinical study.
- Each subject participating in this clinical study will be made aware of the fact that his or her participation involves research and the intent of the research, the expected duration of his or her participation and a description of the procedures that will be followed.
- Each subject will be made aware of the reasonably expected benefits he or she might receive, as well as any risks or potential discomfort that are involved.
- Each subject will also be made aware of alternative treatments available to him or her.
- Each subject will be made aware that his or her records will remain confidential, but that the FDA and the IRB has the right to inspect his or her records.
- Each subject will be told that his or her participation in the clinical study is voluntary, without force or influence from the investigator or sponsor.
- Each subject will be given the name and method of contacting the appropriate person(s) to answer his or her questions about the research and in the event of a research-related injury.
